STUDY PROTOCOL PLAN AND STADISTICAL ANALYSIS PLAN (SAP)

UNIVERSITY CEU CARDENAL HERRERA

Principal investigator: [name] [name]

TITLE: Textural Analysis and Effect of ROI Size on Infrared Thermography in Athletes With Patellar Tendinopathy. A Cross-sectional Study

Research and Ethics Committee of University Católica San Antonio, Number: CE111803

NCT ID:

DATE: 07-23-2025

STUDY PROTOCOL PLAN

Objectives:

The objectives of our study have been the following:

The objectives of this study were: (1) to evaluate differences in thermal and GLCM-based textural features between athletes with PT and healthy controls; (2) to compare the diagnostic performance of IT and GLCM features applied to thermographic images; and (3) to identify the most appropriate ROI size for optimal characterization of PT using both thermal and textural analysis.

Volunteers who want to participate in the study will read the general information of the study and sign the informed consent to participate in the study.

Once the informed consent has been read and delivered, the evaluator will check that they meet the inclusion criteria.

Participants will be divided into two groups: (1) athletes with unilateral PT, diagnosed using a combination of clinical criteria, specific functional tests, and ultrasound evaluation. Additional inclusion criteria for this group included a symptom duration of more than 3 months, a VISA-P score of less than 80, and a differential diagnosis to rule out other possible causes of anterior knee pain; (2) healthy volunteer athletes, recruited under the inclusion criteria of no previous history of PT and a VISA-P score of 100.

Participants with any other lower limb pathology, nerve or vascular disorder, or skin lesion in the knee area that could alter the thermal information of the patellar tendon region will be excluded from both groups.

All participants were instructed not to engage in physical exercise; not to drink alcohol, coffee or energy drinks 12 hours before the measurements; not to smoke in the previous 6 hours; not to apply creams or lotions to their legs to avoid altering skin emissivity; to report any medication or treatments they were taking; and to try to avoid altering their rest and meal habits. These requirements minimise the influence of individual extrinsic factors on the IT results.

Recorded variables

Demographic and clinical characteristics (gender, age, BMI, and duration of evolution) will be recorded. The severity of patellar tendinopathy will be measured using the widely accepted and valid Victorian Institute of Sport Assessment-Patella (VISA-P) questionnaire. All thermal image recordings were performed by the same researcher.

Determination of sample size

The sample size will be calculated using G*Power v.3.1.9.7 software (Heinrich-Heine University) for a logistic regression design to evaluate the diagnostic accuracy of IT in distinguishing between patients with PT and healthy controls, taking into account the possible inclusion of covariates. The parameters are set as follows: odds ratio = 5, alpha error probability $\alpha = 0.05$, power $1-\beta = 0.80$, R^2 for other covariates = 0.1, binomial distribution with a proportion $\pi = 0.5$.

Image acquisition protocol

TI images will be recorded with an OPTRIS PI 450 IRT camera coupled to Optris PI Connect software (Germany). The IRT camera has a noise equivalent temperature difference <40 mK with a field of view of $38^\circ \times 29^\circ$, a wide temperature range of -20 °C to $+100$ °C, a spectral range of $7.5-13$ μ m, a focal plane array sensor size of 382×288 pixels, an emissivity set to 0.98, and a measurement uncertainty of $\pm 2\%$ of the global temperature reading. The capture frame size was 55.4×40.63 cm (1.5 mm/px).

The participant will acclimatise in an isolated room (3.86×3.47 m²), without temperature sources, at an average temperature of (23.7 ± 0.9 °C) and relative humidity of ($49 \pm 5\%$) for 15 minutes without clothing on the lower extremities. The participant will sit on a hydraulic stretcher with their feet on a step to isolate contact with the floor, and the camera will be positioned perpendicular to the subjects for a more accurate reading. Two rectangular ROIs will be selected on each knee using a previously described method by superimposing ROIs on thermal images using markers on the skin. a) an ROI of the patellar tendon (tendon ROI); b) an ROI of the anterior part of the knee (knee ROI) using the anatomical references of the upper pole of the patella, anterior tibial tuberosity, and lateral contour of the knee.

Statistical Analysis Plan (SAP)

The data will be analysed using IBM SPSS Statistics for Windows v.25.0 (IBM Company, 2017). The normality and homoscedasticity of the variables will be checked. The data will be summarised using absolute and relative frequencies for categorical variables, and means \pm standard deviations (SD) and 95% confidence intervals for continuous variables.

Independent sample t-tests will be used to compare continuous variables, and a chi-square test will be used to compare categorical variables at baseline between PT patients and controls.

One-way analysis of covariance will be used to analyse the thermal difference and textural characteristics between PT patients and healthy controls, controlling for the effects of clinical and demographic covariates. Cohen's d statistic will be calculated to assess the effect size (d > 0.1 small, around 0.3 medium, and >0.5 large).

To calculate the diagnostic accuracy of the thermal difference and textural characteristics based on first- and second-order statistical analysis, simple logistic regression will be performed for age, sex, and BMI by group, including them in subsequent models if $p < 0.20$. Sensitivity (Se), specificity (Sp) and Youden's index (expressed as $Se + Sp - 1$) will be investigated, as well as the positive and negative likelihood ratios (LRp and LRn) of thermal difference, textural characteristics and their combinations. The thermal difference and textural characteristics will be introduced one by one and in all possible combinations (255 models) in the logistic regression analyses, including a maximum combination model containing all characteristics.

Receiver operating characteristic (ROC) curves will be used and the Hosmer-Lemeshow goodness-of-fit test will be performed by comparing the observed and expected frequencies of the outcome variable ($p > 0.05$ indicates a good fit). The Brier score will be calculated to evaluate the accuracy of the probabilistic predictions, where lower scores indicate better model performance. An area under the curve (AUC) value close to 90% and sensitivity and specificity values above 80% are considered acceptable.

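### Objectives 2 (IT versus GLCM) and 3 (ROI size) are within-participant comparisons, but the SAP defines no paired difference or confidence interval for either and does not mention ROI

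*Combined protocol and SAP*

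**What the plan says.** The title announces ROI size as a subject of the study: "Textural Analysis and Effect of ROI Size on Infrared Thermography in Athletes With Patellar Tendinopathy". Under Objectives, the second aim is "to compare the diagnostic performance of IT and GLCM features applied to thermographic images" and the third is "to identify the most appropriate ROI size for optimal characterization of PT using both thermal and textural analysis".

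The image acquisition section draws two regions on each knee: "an ROI of the patellar tendon (tendon ROI); b) an ROI of the anterior part of the knee (knee ROI". Every participant therefore supplies both ROIs, and both marker types are read from the same images.

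The sample size section targets something else. It is set up "to evaluate the diagnostic accuracy of IT in distinguishing between patients with PT and healthy controls", which is neither a method difference nor an ROI difference.

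The SAP contains:
- Group comparisons: t-tests and chi-square tests at baseline, then "One-way analysis of covariance will be used to analyse the thermal difference and textural characteristics between PT patients and healthy controls", with Cohen's d.
- Accuracy of each logistic model: sensitivity, specificity, Youden's index, likelihood ratios, ROC curve, Hosmer-Lemeshow test and Brier score. The features enter as follows: "The thermal difference and textural characteristics will be introduced one by one and in all possible combinations (255 models". One of these models holds every feature.
- One absolute criterion: AUC near 90%, with sensitivity and specificity both over 80%.

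The only confidence interval mentioned is a descriptive one for continuous variables. ROI does not appear in the SAP.

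**The concern.** Objectives 2 and 3 ask which of two things measured in the same people performs better. That calls for an estimate of the difference and its uncertainty, allowing for the pairing. The SAP supplies neither. For objective 2 it gives the ingredients of a side-by-side reading. For objective 3, a title claim, it states no analysis.

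At stake is whether a statement that one ROI is the better one can be supported. If the two are close, ranking observed accuracies still names a winner, and nothing in the planned output tells the reader whether the gap exceeds sampling error.

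**Working it through.** **1. Is there an ROI dimension in the model count?** 2^8 − 1 = 255, so the stated number fits all subsets of eight features. Fitting the set once per ROI would give 2 × 255 = 510 models. Mixing both ROIs would give 2^16 − 1 = 65,535. The text does not say which ROI supplies the eight features, or how they divide between thermal and GLCM.

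**2. What sample size is implied?** No N is stated, so there is no figure to reproduce. The stated inputs are odds ratio 5, alpha 0.05, power 0.80, R² 0.1 and binary predictor with proportion 0.5. The null event probability and the sidedness are not given. I took 0.2–0.5 and one- or two-sided tests.
- Upper end (two-sided, null probability 0.5, Wald formula): p2 = 0.833; variance term 1/(0.5 × 0.25) + 1/(0.5 × 0.139) = 22.4; N = (1.960 + 0.842)² × 22.4 / (ln 5)² / 0.9 = 7.85 × 22.4 / 2.59 / 0.9 ≈ 76.
- Lower end (one-sided, null probability 0.3, variance-corrected): v0 = 16.0, v1 = 18.7; N = (1.645√16.0 + 0.842√18.7)² / 2.59 / 0.9 ≈ 45.

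That is roughly 22–38 per group. I use 30.

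**3. How large is a chance gap between two equally good ROIs?** A closed-form check uses the Hanley-McNeil variance with AUC A = 0.80 and n = 30 per group:
- Q1 = A/(2 − A) = 0.667; Q2 = 2A²/(1 + A) = 0.711.
- Variance = [0.16 + 29(0.667 − 0.64) + 29(0.711 − 0.64)]/900 = 0.00333.
- SE of the difference = √[2 × 0.00333 × (1 − r)], where r is the correlation of the two AUC estimates.
- At r = 0.5 the SE is 0.058, and a gap of 0.05 or more occurs in about 39% of studies. At r = 0.7 the SE is 0.045, giving about 26%.

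**4. Simulation.** Paired binormal single features, 30 per group, DeLong interval. The correlation here is between the feature values in the two ROIs. AUCs and correlations are assumptions.

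| True AUCs | Quantity | Correlation 0.5–0.8 | Correlation 0.9–0.95 |
|---|---|---|---|
| 0.80, 0.80 | observed gap of 0.05 or more | 20–42% | about 8% and 2% |
| 0.80, 0.80 | 95% half-width of the difference | 0.08–0.12 | 0.04–0.06 |
| 0.85, 0.80 | ranking is right | 80–92% | 96–99% |
| 0.90, 0.80 | ranking is right | 97% or more | 97% or more |

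For equal AUCs and correlation 0.5–0.8, the chance gap is about 28–46% at 22 per group and 16–33% at 38. With equal AUCs the DeLong interval wrongly excludes 0 in about 4–6% of runs at correlation 0.5–0.8, so the proposed interval roughly keeps its error rate.

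**5. Can the absolute threshold do the job?** At the Youden cut-off with 30 per group, exactly one ROI passes the sensitivity and specificity limits in about 13–15% of studies at 0.85 versus 0.80, and in 35–39% at 0.90 versus 0.80. Otherwise both pass or, far more often, neither does. The AUC part of the criterion was not simulated, because no cut-off is given for being near 90%.

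**The case against.** The other side has five fair points.

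- **Objective 2 is not empty.** Features enter one at a time, and lower Brier scores are called better, so thermal and GLCM accuracies can be read side by side. This stands. A reader might infer that objective 2 has no analysis at all, and the documents do not support that. What is missing is the difference and its uncertainty.
- **The ROIs probably overlap.** The knee ROI's landmarks suggest that the tendon ROI lies largely inside it, so correlations of 0.9 or more are plausible and chance gaps become small. This stands as a limit on the size. The documents give no correlation, however, and a paired interval would show the reader which case applies.
- **The threshold helps.** It does when the gap is large, and then it nearly always favours the better ROI (the worse one passes alone in about 1% at 0.90 versus 0.80). A reader might infer that it is useless, and that is too strong. It is still silent in most studies.
- **Objective 3 speaks of characterisation, not accuracy.** Cohen's d could serve that, so AUC need not be the only yardstick. This stands, but the SAP does not plan Cohen's d by ROI either.
- **The model with every feature could give one answer for thermal and texture together.** It could, if run in each ROI. The SAP does not state that use, so it is an ingredient for the fix and not an existing analysis.

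**Conclusion.** The gap is real and can be seen by setting the Objectives beside the SAP: two paired questions, no paired contrast, no interval for one, and no ROI analysis. It should be fixed before conclusions on objectives 2 and 3 are drawn. Objective 1 and the per-model accuracy results are unaffected.

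The structural finding rests on no assumed figure. The size of the consequence does: group size, true AUCs and between-ROI correlation are all assumptions. Near equality, a gap of 0.05 or more arises by chance in anything from about 2% to 42% of studies with 30 per group, depending mainly on the correlation.

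Two stronger readings are not supported. One is that ranking the ROIs would usually mislead. With a true gap of 0.10 it is right in 97% or more of studies, and with 0.05 in at least about 80%. The difficulty is that the planned output does not reveal which situation holds. The other is that the data had already been examined when the plan was written. The past tense of "All thermal image recordings were performed by the same researcher" might suggest it, but the acquisition section describes recording images in the future tense, and mixed tense alone shows little.

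**What to change.** In the SAP:

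1. Run the same prespecified thermal and GLCM features or models, with the same fixed covariates, in both ROIs. State which ROI the 255 models use.
2. Objective 2: report the paired AUC difference, GLCM minus thermal, within each ROI, with a 95% confidence interval.
3. Objective 3: report the paired AUC difference, tendon minus knee ROI, with a 95% confidence interval. The already planned model with every feature, run in each ROI, can be the single primary contrast, since the objective asks for one answer from both kinds of analysis. Give Cohen's d by ROI beside it for characterisation.
4. Use DeLong for single features. For multi-feature models, or where covariates are screened at p < 0.20, use a participant-level bootstrap with optimism correction and repeat any selection inside it.
5. Do not state that one method or ROI is better when the interval includes 0.

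The cost is SAP wording and some extra analysis of the same images, with no new participants or measurements. The bootstrap is more than a few lines of work. The team should check whether SPSS v.25.0 can do it and, if not, name a second program.

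The downside is low precision. At 30 per group the 95% half-width for single features is about 0.08–0.12 AUC at correlation 0.5–0.8 and about 0.04–0.06 at 0.9–0.95, and it is wider with model selection. The study may have to report no clear winner.

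### The title and Objective 3 ask about ROI size, but the two ROIs also differ in the tissue they sample and the SAP never compares them, so a difference cannot be credited to size

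*Combined protocol and SAP*

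**What the plan says.** The title is "Textural Analysis and Effect of ROI Size on Infrared Thermography in Athletes With Patellar Tendinopathy". Under Objectives, the third aim is "to identify the most appropriate ROI size for optimal characterization of PT using both thermal and textural analysis".

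The section on the image acquisition protocol states: "Two rectangular ROIs will be selected on each knee". The first is the tendon ROI. The second is "an ROI of the anterior part of the knee (knee ROI) using the anatomical references of the upper pole of the patella", together with the tibial tuberosity and the lateral edge of the knee. Both are set by anatomy, and placement follows a method described elsewhere. No width, height or pixel count is given for either, although the image scale is: "The capture frame size was 55.4×40.63 cm (1.5 mm/px").

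In the Statistical Analysis Plan section, the group comparison is: "One-way analysis of covariance will be used to analyse the thermal difference and textural characteristics between PT patients and healthy controls". The diagnostic analysis is a set of 255 logistic models, with ROC curves, sensitivity, specificity, likelihood ratios and Brier scores. That section does not mention ROIs. It has no ROI term, no paired comparison of ROIs and no rule for preferring one ROI over the other.

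**The concern.** The objective and title name size as the factor of interest. The two ROIs do not vary size alone: going from the tendon to the anterior knee enlarges the window and also brings in skin over the patella and the rest of the front of the knee.

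Suppose the tendon ROI discriminates better. That could be because a smaller window is better, or because the useful signal lies over the tendon and the added skin dilutes it. Suppose the knee ROI does better. That could be because more pixels give steadier texture measures, or because tissue outside the tendon carries signal. Each explanation gives different advice to someone choosing an ROI elsewhere, so a report that credits the difference to size could mislead.

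The SAP adds a second gap. Because no comparison between ROIs is specified, even the contrast that the data can support would be judged informally, from two separate sets of results.

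**Working it through.** This is a question of design. It does not depend on sample size, power or alpha, and the plan states no figure to reproduce.

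**Inputs from the document.** Two ROIs per knee, one on the tendon and one on the anterior knee (image acquisition section). The target is ROI size (title and Objective 3). There are 255 models and no ROI term (SAP section).

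**Step 1: can size and region be separated?** Let D be any performance measure for an ROI, such as its AUC. Let s be the effect of a larger window and r the effect of including tissue beyond the tendon. Under an additive model with baseline a:

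- tendon ROI: D_T = a
- knee ROI: D_K = a + s + r

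The only available contrast is D_K − D_T = s + r. The design matrix, with rows (1, 0, 0) and (1, 1, 1), has rank 2 for 3 parameters, so s and r are fully aliased. More participants estimate the sum more precisely but do not split it.

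**Step 2: what would separate them?** Add a tendon-sized window elsewhere on the anterior knee, W, with D_W = a + r. The rows are now (1, 0, 0), (1, 1, 1) and (1, 0, 1), and the rank is 3. Then D_K − D_W = s and D_W − D_T = r. A second size confined to the tendon also breaks the link, because it varies s with r held at zero. It does so only over the range of sizes that fit within the tendon. Both rest on the additive model.

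**Step 3: would a nested series do it?** Take rectangles growing from a tendon ROI of area A_T out to the knee ROI. If the tendon ROI holds only tendon, a rectangle of area A has a non-tendon share of 1 − A_T/A. That share is fixed once A is fixed, so size and tissue still move together, and any separation would come only from an assumed curve shape. Such a series describes the best extent around the tendon; it does not isolate size.

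**Step 4: how far might the sizes differ?** The document gives no dimensions, so this is illustration only. Assume tendon ROIs of 20×30 to 30×50 mm and knee ROIs of 80×100 to 120×140 mm. At 1.5 mm per pixel, pixels = area / 1.5²:

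- tendon: 600/2.25 = 267 to 1500/2.25 = 667
- knee: 8000/2.25 = 3556 to 16800/2.25 = 7467
- ratio: 3556/667 = 5.3 to 7467/267 = 28

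On these assumptions the pixel count changes about 5- to 28-fold at the same step as the tissue.

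**Step 5: does the model set contain an ROI comparison?** 255 = 2⁸ − 1, which is every non-empty subset of eight characteristics. The SAP does not list the eight or say from which ROI they come. Running the set once per ROI would give 2 × 255 = 510 fits, but this is not stated, and no step then compares the ROIs.

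**The case against.** The strongest reply is that ROI size is a reasonable shorthand for extent. On a fixed body region, a larger window always takes in neighbouring tissue, and a user mainly wants to know whether to draw tightly round the tendon or take the whole front of the knee. The plan claims no mechanism. Objective 3 asks for the most appropriate size, which can mean the better of two candidates, and the word optimal describes the characterization of PT, not the size. This largely stands. It means that the objective has a practical reading which the data can serve, and that the plan cannot be charged with promising a search over all sizes. It does not rescue wording that names size as the cause, or supply the missing comparison.

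A second reply is that the document never states that the ROIs differ in size, and that dimensions may be in the cited placement method. This is also fair. The difference in extent is inferred from the landmarks and the title. Dimensions found elsewhere would describe the size contrast but would not remove the aliasing while there are only two ROIs.

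A reader might infer that Objective 3 cannot be answered at all, or that the ROI results will be worthless. The document does not support that: both ROIs are taken on every knee, so a within-person comparison of the two is available.

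**Conclusion.** The point holds in a limited form. The plan can establish which of the two defined ROIs discriminates better between athletes with PT and controls, once a comparison is specified. It cannot attribute a difference to size, and it cannot identify a best size beyond the two examined. The aliasing is complete (rank 2 for 3 parameters) and does not shrink with sample size.

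The reach is one objective of three, plus the title; Objectives 1 and 2 are untouched by this point. The conclusion assumes that the knee ROI is the larger and takes in tissue outside the tendon, as its landmarks imply, and that no further ROIs are planned beyond those described. The pixel ratios are illustrative and carry no weight in the conclusion.

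**What to change.** **Minimum change.** Restate Objective 3 and the title as tendon ROI versus anterior-knee ROI, and limit the conclusions to that contrast. In the SAP, pre-specify a paired comparison of AUCs between the two ROIs, by DeLong's test or by a bootstrap that resamples participants so that both ROIs from one person stay together. Use the same model, named in advance, in each ROI. Comparing the best of 255 in one ROI with the best of 255 in the other would mix model selection with the ROI effect.

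**If a claim about size is to be kept.** Also extract from the same images at least one pre-set window that separates size from region: a tendon-sized window elsewhere on the anterior knee, or a second size confined to the tendon. Give the dimensions of every window in pixels or mm. A nested series out to the knee ROI may be added, but should be reported as a search for the best extent around the tendon.

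**Cost.** The first option costs a narrower claim, some wording and one added analysis. The second costs some re-cropping and a few more comparisons, which should be named in advance. It needs no new participants or imaging, provided the images are retained. The document does not say whether they are, so that is an assumption.

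### The stated 0.80 is power to detect an odds ratio of 5, not power or precision for the AUC/Se/Sp benchmark, and that benchmark is set for 255 models fitted in the same data with no interval or optimism correction named

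*Combined protocol and SAP*

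**What the plan says.** The section on determination of sample size describes a G*Power calculation "for a logistic regression design to evaluate the diagnostic accuracy of IT in distinguishing between patients with PT and healthy controls". It continues: "The parameters are set as follows: odds ratio = 5", followed by alpha 0.05, power 0.80, R² of 0.1 for other covariates, and a "binomial distribution with a proportion" of 0.5. It gives no resulting N, no sidedness, no baseline probability and no allocation ratio. It does not name the predictor to which the odds ratio applies.

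The Statistical Analysis Plan names "95% confidence intervals for continuous variables" among the descriptive summaries. It says "Sensitivity (Se), specificity (Sp) and Youden's index" will be examined, together with likelihood ratios. The thermal difference and textural features enter singly and "in all possible combinations (255 models) in the logistic regression analyses". The last paragraph sets the standard: "An area under the curve (AUC) value close to 90% and sensitivity and specificity values above 80% are considered acceptable". No interval is named for AUC, sensitivity or specificity. No rule is given for choosing a cut-off or a model, and no internal validation or optimism correction is described.

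**The concern.** A reader will take the 0.80 as assurance about diagnostic accuracy, which the second objective concerns. No AUC, sensitivity, specificity or interval width enters the calculation, so the 0.80 says nothing about the chance of meeting the benchmark or about the precision around it.

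As written, the benchmark attaches to the estimates alone. In groups of modest size, an estimate just above 80% can come from a marker whose true value is far lower. Judging models on the data used to fit them, especially the best of 255, pushes the apparent figures upward. A marker could then be called acceptable when the data do not support it.

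**Working it through.** The plan states no N, so there is no figure to reproduce. The inputs are those listed in the sample-size section. Everything else is marked as an assumption.

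**1. What N the inputs imply.** Read the binomial setting as a binary predictor X with P(X=1) = 0.5, and assume half the participants are cases. Then P(case | X=0) = 1/(1+√5) = 0.309 and P(case | X=1) = 0.691. The two-sided Hsieh formula, with the covariate allowance, is

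N = [z(0.975)·√(P(1−P)/π) + z(0.80)·√(p₁(1−p₁) + p₂(1−p₂)(1−π)/π)]² / [(p₁−p₂)²(1−π)] ÷ (1−R²)

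= (1.386 + 0.550)² / (0.382² × 0.5) ÷ 0.9 = 51.4 ÷ 0.9 = 57.1.

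The Wald version gives 63.1. Rounded up across formulas, the total is 57–64 two-sided and 45–50 one-sided. With baseline probabilities from 0.1 to 0.6, which make the groups unequal, it is 57–105 two-sided and 45–83 one-sided. I use 30 per group below as an assumption.

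**2. What an odds ratio of 5 means for accuracy.**
- Binary predictor: OR = [Se/(1−Se)]·[Sp/(1−Sp)]. The smaller of Se and Sp is greatest when they are equal: √5/(1+√5) = 69.1%. Se = Sp = 80% would need OR = (0.8/0.2)² = 16.
- Normal marker, OR = 5 per within-group SD: separation ln 5 = 1.609, AUC = Φ(1.609/√2) = 0.872, Se = Sp = Φ(1.609/2) = 79.0%.
- Normal marker, OR = 5 per total SD: AUC 0.828, Se = Sp = 74.8%.

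On each reading the 0.80 is the chance of rejecting OR = 1.

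**3. Precision at 30 per group.** The smallest count above 80% is 25/30.
- Exact 95% interval for 25/30: 65.3–94.4% (half-width 14.5 points). For 27/30: 73.5–97.9% (12.2 points).
- At other assumed sizes: 18/22 gives 59.7–94.8%, and 26/32 gives 63.6–92.8%.
- Hanley–McNeil AUC half-width: 1.96 × 0.0577 = 0.113 at AUC 0.80, and 1.96 × 0.0417 = 0.082 at AUC 0.90.

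**4. Chance that both estimates exceed 80%** (fixed cut-off, 30 per group): P(Bin(30, p) ≥ 25)².

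| True Se = Sp | Both above 80% |
|---|---|
| 69.1% | 0.4% |
| 75% | 0.203² = 4.1% |
| 80% | 18% |
| 85% | 50% |
| 90% | 86% |

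**5. Selection over 255 models.** Since 255 = 2⁸ − 1, eight features are implied. The assumed scenario is one marker with true AUC 0.80, seven independent noise features, 30 per group, logistic fits, the Youden cut-off, and the model with the highest AUC taken. In 472 runs:
- mean apparent AUC 0.855, true 0.754;
- apparent Se/Sp 0.805/0.823, true 0.667/0.692;
- both above 80% in 18.6% of runs;
- the ordinary 95% interval for AUC covers the true value in 44.5% of runs.

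A repeat with separate code (300 runs) gave 0.857 against 0.755, 17% and 44%. Also requiring AUC of at least 0.88 or 0.90 lowered the proportion meeting the benchmark to about 16% or 12% (309 runs). The single marker with its own Youden cut-off has both above 80% in 3.3% of 20,000 runs, with no AUC condition, so it compares with the 17–19%.

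**The case against.** The best defence is that an odds ratio of 5 is a legitimate minimum detectable association, that a logistic calculation matches the logistic models planned, and that the benchmark is a descriptive label with no hypothesis attached, so no power is owed for it. That stands. It does not make the 0.80 a statement about accuracy, and it does not supply the missing intervals.

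Several stronger readings are tempting, and the documents do not support them:
- *The sample size is miscalculated.* No N is stated and no printed figure is contradicted.
- *The design rules out meeting the benchmark.* The 69.1% ceiling needs the binary reading. On the per-SD reading, OR = 5 lies near the benchmark. On either reading it is only the effect powered for, and the true effect may be larger.
- *A marker with true values of 75% passes one time in five.* That 20% is sensitivity alone. Both measures pass together in about 4% of samples.
- *Selection multiplies false acceptance twelvefold.* That sets a Youden cut-off (19%) against a fixed one (1.6%). Like for like it is 17–19% against about 3%.
- *The best of 255 will be the result reported.* The SAP gives no selection rule, so this is a risk left open.

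It is also fair to say that the simulation is one scenario, with seven pure noise features that the documents do not suggest, and that naming Youden's index hints at the cut-off. If the index does set it, the cut-off is chosen in the same data and the case for correction is stronger.

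**Conclusion.** The point holds as a mismatch between power and purpose, with uncorrected selection added. Two facts rest on the text alone. The inputs power a test of OR = 1 for one predictor, and the SAP names no interval and no optimism correction for the measures that it judges. That apparent accuracy is biased upward for a model or cut-off chosen in the same data is a general result.

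The size is less certain. It rests on an assumed 30 per group, equal groups and, for the selection figures, a single scenario. In that setting an estimate just above 80% is compatible with a true value of about 65%. The best of 255 models overstates AUC by about 0.10 (0.855 − 0.754), and the ordinary interval misses the true AUC in more than half of runs. An ordinary interval alone would therefore not cure the selection problem. The change should be made. It does not imply that the study needs more participants.

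**What to change.** 1. In the sample-size section, state that 0.80 is power to detect OR = 5 for a single predictor, which should be named, and is not power for the accuracy benchmark. Give the expected 95% half-widths for Se, Sp and AUC at the N used. At an assumed 30 per group these are about 15 points at 25/30, 12 points at 27/30, and 0.08–0.11 for AUC.
2. In the SAP, report Se, Sp and AUC with 95% intervals and interpret *acceptable* alongside the interval. No lower-limit threshold is proposed, because the documents give no basis for one.
3. For any cut-off or model chosen in the same data, report optimism-corrected AUC, Se and Sp from a bootstrap that repeats the cut-off choice and the 255-model selection in each resample. Otherwise label the result exploratory.

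The cost is one reworded paragraph, a few added sentences, and some scripting and computing time for the bootstrap; the exploratory label costs almost nothing. The power statement will look less favourable and reported accuracy will be lower. No enrolment is involved, so the changes remain possible if measurement is already complete, as the documents' mixed tenses leave open.
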